10.3 Important Protocol Deviations

Important Protocol Deviations (IPDs) categories are defined by the study team before the first subject's visit and updated during the IPD reviews throughout the study prior to database lock. These definitions of IPD categories, sub-category codes and descriptions will be used during the course of the study.

Eligibility deviations are defined in the protocol. Eligibility deviations that are defined as IPDs will be summarized in both the IPD and Eligibility Deviation table and IPD and Eligibility Deviation listings.

10.4 Demographic and Baseline Characteristics

Summary statistics of the following demographic and baseline disease characteristics will be tabulated using the Safety Analysis Set for phase 1b and Full Analysis Set for phase 3.

- Region (USA or Non-USA)
- Age at enrollment: <50, ≥ 50; < 65, ≥ 65; <75, ≥75 years
- Sex (male or female)
- ECOG performance status (0 vs 1)
- LDH: ≤ ULN vs > ULN; **≤ 2 x ULN vs > 2 x ULN**
- HSV-1 serostatus (positive vs negative vs missing/unknown)
- Individual disease stage per eCRF (stage IIIB, IIIC, IVM1a, IVM1b, and IVM1c)
- Grouped disease stage per IVRS and CRF (less advanced vs more advanced): IIIB/C-IVM1a vs IVM1b/c (CRF and IVRS)
- Grouped disease stage: IIIB/C-IVM1b vs IVM1c
- **Baseline** PD-L1 status (positive, negative, vs indeterminate/unknown)
- Interval from initial melanoma diagnosis and enrollment / randomization
- The sum of longest, or shortest for nodal, diameters of target lesions (SLD) determined by BICR (both continuous and dichotomized group based on median will be presented)
- *BRAF* mutation status (V600E/K mutation present, no mutation, or unknown)
- Prior BRAF inhibitor (yes versus no BRAF inhibitor with or without MEK inhibitors) (IVRS)
- Prior BRAF inhibitor (none, BRAF inhibitor alone, BRAF and MEK inhibitors in combination): if subjects included in each of the 2 BRAF related category represent ≥ 10% of the study population (CRF)
- Baseline *BRAF*^{V600} mutation: yes vs no vs missing/unknown
- **Treated brain metastasis (yes vs no)**
- **Liver metastasis (yes vs no)**
- **In-transit metastases (yes vs no)**
- **IVM1c with no visceral lesions (yes vs no)**
- *BRAF*^{V600} status (*BRAF* wild type vs *BRAF*^{V600} mutant, previous directed treatment vs *BRAF*^{V600} mutant, no previous directed treatment)
- **Previous adjuvant or neoadjuvant therapy (yes vs no)**

10.5 Efficacy Analyses

The following sections describe analyses of efficacy endpoints for phase 1b and phase 3, separately. Analysis sets used for efficacy endpoints will be specified accordingly.

10.5.1 Phase 3

Analysis of efficacy endpoints will be based on the Full Analysis Set.

10.5.1.1 Analyses of Primary Efficacy Endpoint(s)

The primary analyses of the dual primary endpoints of PFS and OS will be triggered when 407 PFS events and 346 OS events have occurred, respectively, as well as OS interim analysis at 282 events (including a futility analysis) **and at 315 events**. The final analysis will occur approximately 5 years (60 months) after the last subject has been enrolled in phase 3.

[figure not shown]
- The analyses of primary efficacy endpoints will be based on stratified log-rank tests as a primary method for testing the null hypothesis of no treatment difference.

In order to allow for the use of PD-L1 status in a stratified analysis, indeterminate and missing PD-L1 status will be classified together with the “negative” PD-L1 group and analyze in the categories of “positive” vs “not positive” PD-L1 group.

Hazard ratios and corresponding two-sided 95% CI will be estimated using Cox PH models stratified by randomization stratification factors per IVRS (disease stage [IIIB-IVM1a vs IVM1b/c] and prior BRAF inhibitor therapy [no vs yes]) and the baseline PD-L1 status (positive vs not positive). KM time to event curves will be presented by the randomized treatment group.

Multiple statistical hypothesis tests will be conducted which include testing for primary endpoints of PFS and OS and the 3 secondary endpoints (iCRR, iPFS, and OS in the subgroup excluding disease stage IVM1c) at multiple analysis time points. To control the study-level overall Type I error at an overall 2-sided 0.05 level, a graphic-based multiple testing procedure for group sequential tests for multiple endpoints will be utilized ([Maurer and Bretz, 2013](#)) (see code fragment in [Appendix C](#)). No updated information will be used when a hypothesis is re-tested at a later time point after its primary analysis. A hypothesis can be re- tested repeatedly with a different nominal level that is propagated from rejecting other hypothesis test(s). The following figure illustrates the **Maurer-Bretz** multiple testing procedure with initial 2-sided α allocation specified as a fraction used for each hypothesis test. Each hypothesis is represented by a circle. A 0 fraction in the circle indicates a hypothesis that is tested conditional on rejection of another hypothesis. The fractions in the square on the directed arrows connecting 2 hypotheses indicate the proportion of α propagated to the next hypothesis test(s) when the current hypothesis is rejected.

Figure 1. Initial Graph of Maurer-Bretz Multiple Testing Procedure

$$H_1 \alpha = 0.05 \times 9/10 = 0.045$$
$$H_2 \alpha = 0.05 \times 1/10 = 0.005$$

Due to the nature of the Maurer-Bretz multiple testing procedure, nominal levels used for testing the OS subgroup can range between 0.05% to 5%.

Further details regarding the derivation of nominal significance levels for each hypothesis test at the planned analyses are provided in [Appendix B](#).

OS follow-up time will be assessed overall and by treatment arm. The distribution of actual and potential follow up will be provided (eg, median, range, etc.). Clark's completeness index (C) will be calculated (Clark, 2002) to quantify the actual relative to potential follow up (see code fragment in [Appendix C](#)). Plots of actual follow-up time versus time of study entry will be provided overall and by treatment arm for all subjects to assess observed follow-up times relative to potential follow up, and will be repeated for the subset with censored OS.

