For a full list of study procedures, including the timing of each procedure, please refer to [Section 7](#) and the Schedule of Assessments ([Table 5](#) and [Table 6](#)).

Statistical Considerations:

Phase 1b:

Sample size considerations:

For phase 1b, 6 to 9 evaluable subjects will be required to assess the DLT profile of talimogene laherparepvec in combination with pembrolizumab. Additional subjects, to a total of 20, will be enrolled in the phase 1b portion of the trial to address the secondary objective exploring the relationship between [REDACTED] and response to treatment.

Planned method of analyses:

The efficacy and safety data will be summarized separately for phase 1b and phase 3.

The phase 1b safety analysis is planned when there are 6 to 9 DLT evaluable subjects.

For phase 1b, besides a summary of the incidence of DLTs, descriptive statistics will be provided for demographics, safety, efficacy, and [REDACTED] as appropriate.

Treatment effects in efficacy endpoints in phase 3 will be according to the treatment group as randomized. Frequency and percent of subjects for binary and categorical efficacy endpoints will be summarized by treatment arm. Proportions and 95% confidence interval using a normal approximation will also be provided. Treatment comparisons will be based on Cochran-Mantel-Haenszel test. Exact tests will be used for subgroup analyses when cell sizes are too small. Analysis of time-to-event endpoints will be based on K-M estimation. Hazard ratios (HRs) will be estimated using Cox proportional hazards (PH) model.

Phase 3:

Sample size considerations:

There are 2 primary endpoints, PFS and OS, in phase 3. The hypothesized reduction of 1/3 hazard for PFS (talimogene laherparepvec and pembrolizumab / pembrolizumab and placebo) is equivalent to an HR of 0.67 and the hypothesized HR for OS is 0.70. Initial allocation of significance level, overall 2-sided 0.05, is 2-sided 0.005 for PFS and 2-sided 0.045 for OS. The event goal for PFS to achieve 90% power at 2-sided 0.005 is 407. The event goal for OS adjusted for 4 group sequential analyses to achieve 90% power at a 2-sided 0.045 is 346. The sample size is 660 subjects (ie, 330 per arm) based on an estimate of 346 death events occurring within 5 years (60 months).

Planned method of analyses:

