10.1.3 Covariates and Subgroups

Randomization will be stratified by stage of disease: less advanced stages (IIIB, IIIC, and IVM1a) versus more advanced stages (IVM1b and IVM1c) and by prior BRAF inhibitor therapy: no prior BRAF inhibitor versus prior BRAF inhibitor with or without MEK inhibitor.

[figure not shown]
The following baseline covariates and randomization stratification factors may be used to examine efficacy in subgroups or in multivariate analyses:

[figure not shown]
- Region, if applicable (USA or non-USA)
- Age: < 50, ≥ 50; < 65, ≥ 65; < 75, ≥ 75 years
- Individual disease stage: IIIB vs IIIC vs IVM1a vs IVM1b vs IVM1c
- Grouped disease stage: IIIB/C-IVM1a vs IVM1b/c (CRF and IVRS)
- Grouped disease stage: IIIB/C-IVM1b vs IVM1c
- LDH: ≤ ULN vs > ULN
- Sex (female vs male)
- ECOG performance status (0 vs 1)
- HSV-1 serostatus (positive vs negative)
- The sum of longest, or shortest for nodal, diameters of target lesions (SLD) **determined by blinded independent central review (will be dichotomized based on median)**
- **Baseline PD-L1 status (positive vs not positive)**
- Prior BRAF inhibitor (none vs BRAF inhibitor alone vs BRAF and MEK inhibitors in combination): if subjects included in each of the 2 BRAF related category represent ≥ 10% of the study population (CRF)
- Prior BRAF inhibitor (yes versus no BRAF inhibitor with or without MEK inhibitors) (IVRS)
- **Baseline of BRAF^{V600} mutation: yes vs no vs missing/unknown**

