10.2 Sample Size Considerations

10.2.1 Sample Size Considerations for Phase 1b

Six to nine DLT-evaluable subjects will be required to assess the DLT profile of talimogene laherparepvec in combination with pembrolizumab for phase 1b. The sample size of approximately 6 to 9 subjects is determined empirically and is consistent with those used in 6+3 phase 1 designs to evaluate the safety of a single dose of each agent assuming a true incidence rate of DLT is 11 to 33%. Additional subjects, up to a total of 20, will be enrolled in the phase 1b portion of the trial to address the secondary objective exploring the relationship between [REDACTED] and response to treatment.

[figure not shown]

10.2.2 Sample Size Considerations for Phase 3

There are 2 primary endpoints for phase 3, PFS and OS. A 1/3 reduction in hazard ratio (talimogene laherparepvec with pembrolizumab / placebo with pembrolizumab) for PFS (HR = 0.67), and a hazard ratio of 0.70 for OS are hypothesized in the Full Analysis Set. Assuming events follow piece-wise exponential distributions (Figure 1 and Figure 2), the hypothesized HRs will translate into a relative increase of 167% in median PFS time and 44% in median OS time. The absolute increase in median PFS will be 9.4 months (5.6 to 15.0 months) in the talimogene laherparepvec and placebo arm and 12.4 months (28 to 40.4 months) in median OS.

[figure not shown]
Approved

Figure 1. Progression-free Survival

Median PFS (pembrolizumab), 5.6 months; $p(t)$ = event rate at month t ; $p(1.5) = 0.95$; $p(3) = 0.6$; $p(6) = 0.49$; $p(12) = 0.39$; $p(18) = 0.32$; $p(24) = 0.30$; constant hazard in each interval between 2 consecutive pieces; a constant hazard ratio across all pieces.

Figure 2. Overall Survival

Median OS (pembrolizumab) = 28 months; $p(t)$ = event rate at month t ; $p(48) = 0.31$ and $p(60) = 0.27$; constant hazard in each interval between 2 consecutive pieces; a constant hazard ratio across all pieces.

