The overall Type I error for the dual primary endpoints is 2-sided 0.05. The event goal for PFS to achieve 90% power at 2-sided 0.005 is 407 and that for OS to achieve 90% power at a 2-sided 0.045 is 346 after taking into account the group-sequential interim OS analyses. The OS event goal is not adjusted for the non-binding OS futility assessment at the second OS interim analysis. The sample size is 660 (ie, 330 per arm) based on an estimate of 346 death events occurring within 5 years (60 months) with approximately 48% of subjects censored. Assuming a non-uniform subject accrual rate for which 50% of cumulative enrollment is accrued at 2/3 of expected total enrollment period (Lachin and Foulkes, 1986), and exponential distributions for loss to follow up for PFS and OS with an annual rate of 5% for OS and 10% for PFS, Table 9 displays estimated timing of analysis based on the actual enrollment rate:

Table 9. Timing of Primary Analysis for PFS (at 407 events) and OS (at 346 events)

Enrollment Duration (month)	PFS PA DCO (month)	OS Events (% event goal) at PFS PA DCO	OS PA DCO (month)
26	48	252 (73%)	75

DCO = data cutoff at event goal; OS = overall survival; PA = primary analysis; PFS₁ = progression free survival per blinded independent central review using modified RECIST 1.1.

Analysis timings are further informed by event projection simulations based on KEYNOTE-006 year 4 data for all subjects in the pembrolizumab arm. Analysis timings assume the hypothesized constant hazard ratio of 0.67 for PFS and 0.70 for OS (see Table 10 below).

[figure not shown]
In addition to hypothesis tests for the dual primary endpoints, statistical tests of the secondary endpoints, iCRR and iPFS, by blinded independent central review using

modified irRC-RECIST, and OS in the disease subgroup excluding IVM1c, will be performed. [Table 10](#) shows event goals (or analysis time) based on hypothesized effect sizes and simulated powers for testing 5 endpoints, where PFS and iPFS refer to the modified RECIST 1.1 and modified irRC-RECIST criterion, respectively. The simulated powers are based on the Maurer-Bretz graphic-based multiple testing procedure ([Maurer and Bretz, 2013](#)) assuming a 1-time analysis. Details of the multiple testing procedure are described in [Section 10.5](#).

Table 10. Hypothesized Effect Sizes and Hypothesis Test Powers

Hypothesis	Effect Size	Primary Analysis Timing	Simulated Power ^a
H ₁ (OS)	HR = 0.70	346 events	91%

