10.5.2 Primary Endpoint

10.5.2.1 Phase 1b

Subject incidence of DLT: The subject incidence of DLT will be summarized using the DLT analysis set.

10.5.2.2 Phase 3

The primary analyses of the primary endpoints of PFS and OS will be based on stratified log-rank tests as a primary method for testing the null hypothesis of no treatment difference.

The stratification factors will include randomization factors per IVRS and PD-L1 status at baseline (positive vs not positive). Inclusion of PD-L1 is considered in the stratified analysis because PD-L1 overexpression could be a potential prognostic factor, and its pretreatment status may not be able to be confirmed prior for use as a stratification factor at the time of randomization. In order to allow for the use of PD-L1 status in a stratified analysis, indeterminate and missing PD-L1 status will be classified together with the “negative” PD-L1 group. Hazard ratios will be estimated using Cox proportional hazards (PH) models stratified by randomization factors per IVRS and the baseline

PD-L1 status (positive vs not positive). Kaplan-Meier (KM) time to event curves will be presented by the randomized treatment group.

Statistical testing of a treatment effect for PFS and OS will follow the multiple hypothesis testing procedure as described in [Section 10.5](#).

Subgroups and covariates for analyses of PFS and OS will include, but not limited to, disease stage (IIIB/C to IVM1a, IVM1b/c), known PD-L1 status (positive, negative) and prior treatment with BRAF inhibitor.

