7.9 Subgroup Analyses

Efficacy analyses specified for the Full Analysis Set for phase 3 will be repeated within the following subgroups:

- PD-L1 status (positive, not positive) at baseline
- Disease stage (less advanced [stage IIIB/C-IVM1a], more advanced [stage IVM1b/c]) at baseline (IVRS)
- Prior treatment with BRAF inhibitor (IVRS)
- Region, if applicable (USA or non-USA)
- Age: < 65, ≥ 65; < 75, ≥ 75 years
- LDH: ≤ ULN vs > ULN
- Sex (female vs male)
- ECOG performance status (0 vs 1)
- HSV-1 serostatus (positive vs negative vs missing/unknown)
- The sum of longest, or shortest for nodal, diameters of baseline target lesions (SLD) determined by BICR (**≤ median of SLD vs > median of SLD**)
- Baseline *BRAF*^{V600} mutation (yes vs no vs missing/unknown)

The sum of longest, or shortest for nodal, diameters of baseline target lesions (SLD) will be dichotomized into two groups based on the median calculated at the time of analysis.

[figure not shown]
These subgroups will be re-examined for appropriateness and may be re-categorized or omitted (due to small sample size, for example, if there are < 10% of subjects within a subgroup) before unblinding. The analyses of these subgroups will be exploratory in nature.

The treatment effects in subgroups will be estimated using stratified odds ratio for binary endpoints; and stratified HR for time to event endpoints. Stratification factors in the analysis model will include the randomization stratification factors as well as PD-L1 status at baseline (positive vs not positive). In the case of a subgroup analysis of one of the stratification factors, only the other two stratification factors will be included in the models. To evaluate the efficacy of talimogene laherparepvec in combination with pembrolizumab in subgroups defined by the stratification factors and key covariates, the treatment effect will be investigated using the Gail and Simon quantitative and qualitative interaction tests (1985). Post hoc power for a nominal 2-sided 5% significance level test

may be calculated to help aid in the assessment (see code fragment in [Appendix C](#)).

The adjusted hazard ratio of the treatment effect with the corresponding 95% confidence interval and p-value adjusting for each of the subgroup variables listed above, using the stratified Cox proportional hazards (PH) model, as well as adjusting for all subgroup variables simultaneously in a multiple regression analysis, will be presented.

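### Cheap improvement, not an error: adjusting the primary PFS and OS analyses for baseline LDH, which is already scheduled, could gain a few points of power if LDH is strongly prognostic

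*SAP*

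**What the plan says.** **Primary analysis.** SAP 10.5.1.1 and Protocol 10.5.2.2 use a stratified log-rank test and a stratified Cox model. The factors are "disease stage [IIIB-IVM1a vs IVM1b/c] and prior BRAF inhibitor therapy [no vs yes]) and the baseline PD-L1 status (positive vs not positive", which makes 8 strata. LDH is not among them and no reason is given. SAP 10.5.1.2 carries the same analysis over to iPFS and to OS excluding stage IVM1c.

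**PD-L1.** This factor was not used at randomization. Protocol 10.5.2.2 explains: "Inclusion of PD-L1 is considered in the stratified analysis because PD-L1 overexpression could be a potential prognostic factor". The same sentence adds a second reason, that PD-L1 status might not be known when a subject is randomized. Missing and indeterminate results are grouped with negative.

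**LDH.**
- Phase 3 schedules it within 14 days before enrollment and on day 1 of week 0 (Protocol Table 6, 7.2.1, 7.2.2). SAP section 6 defines a baseline value for dosed and undosed subjects.
- It is a planned covariate, "LDH: ≤ ULN vs > ULN" (Protocol 10.1.3, SAP 4.2), and a subgroup variable (SAP 7.9).
- SAP 7.9 also presents stratified Cox hazard ratios adjusted for each subgroup variable in turn, "as well as adjusting for all subgroup variables simultaneously in a multiple regression analysis".
- It enters the inverse-probability-of-censoring-weighted (IPCW) OS sensitivity analysis (SAP 10.5.4.2).

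**Design.** The alpha "is 2-sided 0.005 for PFS and 2-sided 0.045 for OS" (Protocol synopsis). Effects "for PFS (HR = 0.67), and a hazard ratio of 0.70 for OS are hypothesized" (Protocol 10.2.2). Neither document gives an LDH effect on PFS or OS, or an expected share above ULN.

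**The concern.** If a baseline factor is strongly prognostic and is left out of a Cox or log-rank analysis, the treatment hazard ratio is pulled toward 1. Power then falls for the same number of events. The value is already scheduled, and the plan itself treats LDH as relevant to outcome.

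The LDH-adjusted models that are planned do not address this. Those in SAP 7.9 belong to exploratory subgroup work, and the IPCW model is a sensitivity analysis. Neither can change the confirmatory result. What is at stake is efficiency on both primary endpoints, including PFS, which is tested at only two-sided 0.005.

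**Working it through.** **1. The plan's own figures, without LDH**

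Events needed at 1:1 allocation (Schoenfeld): D = 4(z_α/2 + z_β)² / (ln HR)².

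- PFS, "The event goal for PFS to achieve 90% power at 2-sided 0.005 is 407": 4(2.807 + 1.282)² / (ln 2/3)² = 66.87 / 0.1644 = 407. This matches. The design effect is a one-third reduction, so HR = 2/3. With the rounded 0.67 the formula gives 417 events, and 407 events give 89.1% power.
- OS, "for OS to achieve 90% power at a 2-sided 0.045 is 346 after taking into account the group-sequential interim OS analyses": the fixed design gives 4(2.005 + 1.282)² / (ln 0.70)² = 43.20 / 0.1272 = 340. Lan-DeMets O'Brien-Fleming looks at 252, 282, 315 and 346 deaths give nominal levels of 0.0150, 0.0187, 0.0261 and 0.0336. Cumulative power is 65.5, 75.6, 84.1 and 89.6%. Protocol Table 12 has the same levels and 66, 76, 84 and 90%.

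So there is no shortfall against the stated power.

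**2. Benchmark for the simulations**

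The OS simulations test only at the final look, at 0.0336, with no credit for interim looks. The expected power is Φ(√(346/4) × |ln 0.70| − 2.125) = Φ(3.317 − 2.125) = Φ(1.192) = 88.3%.

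**3. LDH as a Cox covariate, OS**

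All LDH inputs are assumptions. Each cell shows power with the planned strata → strata plus LDH covariate (346 deaths, treatment HR 0.70 within LDH level).

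| LDH HR | A: score test | B: score test | C: Wald test, two prevalence settings |
|---|---|---|---|
| 1.0 | 87.5 → 87.5 | 88.3 → 88.0 | 87.4 → 87.0; 87.0 → 86.9 |
| 1.5 | 87.1 → 87.6 | 85.5 → 86.7 | 86.1 → 87.3; 83.8 → 84.3 |
| 2.0 | 84.4 → 87.3 | 84.5 → 87.0 | 86.3 → 88.0; 86.4 → 88.7 |
| 2.5 | 81.6 → 87.0 | 81.7 → 88.1 | 81.5 → 85.8; 80.0 → 85.7 |

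- A: 660 subjects, 4,000 trials per setting. LDH above ULN in 10% of less advanced and 45% of more advanced stage, stage HR 1.5, PD-L1 HR 0.7.
- B: 660 subjects, a separate run of the same test with an assumed LDH distribution.
- C: 692 subjects (the count in SAP Table 5), 1,500 trials per setting, exponential survival, 25% to 35% above ULN.

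Differences by row: −0.4 to 0.0 points at LDH HR 1.0; 0.5 to 1.2 at 1.5; 1.7 to 2.9 at 2.0; 4.3 to 6.4 at 2.5.

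The simulation standard error of one power figure near 87% is √(0.87 × 0.13 / 4,000) = 0.5 points for A and √(0.87 × 0.13 / 1,500) = 0.9 points for C.

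**4. PFS, covariate form**

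407 events, HR 2/3, level 0.005, simplified exponential curve: 87.9 → 88.1% at LDH HR 1.0, 84.5 → 87.8% at 2.0 and 81.2 → 88.4% at 2.5.

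**5. Type I error**

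With no treatment effect, rejection rates without and with LDH were 3.6 and 3.7%, 3.4 and 3.5% (6,000 trials), and 3.3 and 3.6% in a separate run. The standard error for 6,000 trials at the 3.36% level is √(0.0336 × 0.9664 / 6,000) = 0.23 points.

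**6. LDH as a fourth stratum instead (16 strata)**

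This used the protocol's control curves, accrual and dropout, with 4,000 trials per setting. OS power was 87.6 → 86.7% at LDH HR 1.0, 86.2 → 86.0% at 1.5, 84.0 → 86.3% at 2.0 and 82.4 → 86.9% at 2.5. Doubling the strata costs about 1 point when LDH has no effect. That is why the covariate form is preferred.

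**The case against.** **Power.** A reader might infer that the trial is underpowered, or gives up power for nothing. The documents do not support that. The event goals reproduce, and Protocol 10.2.2 states 0.67 and 0.70 for the Full Analysis Set without saying that they hold within LDH level. If they are the effects under the planned analysis, LDH would add power above 90% rather than restore it. The drift of the unadjusted OS estimate from 0.70 to about 0.72, seen in simulation C at LDH HR 2.5, has the same dependence. This stands.

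**PD-L1 parallel.** A reader might infer that the reason for adding PD-L1 applies equally to LDH. It does so only in part. Possible non-availability at randomization was also given, and LDH was scheduled at screening and not chosen as a randomization factor. This stands.

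**Unknown size.** The stage strata may already carry part of any LDH effect. The eligibility rule requiring LDH below ULN in BRAF-mutant or unknown subjects without a prior BRAF inhibitor lowers the share above ULN, and it is not evidence of prognosis. The simulations are noisy between settings: in C, unadjusted power rises from 83.8 to 86.4% as the LDH HR goes from 1.5 to 2.0. The with-and-without comparison within a setting is less affected.

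**Existing use.** LDH-adjusted estimates will be reported, both singly and jointly. That is true, but they do not feed the confirmatory test.

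**Costs.** The Full Analysis Set is all randomized subjects, and a Cox covariate drops missing values unless a rule prevents it. A schedule does not show that every subject has a value. SAP 9.6 describes the log-rank as fully non-parametric; the replacement is not. ECOG, target-lesion size and stage IVM1c are planned covariates too, and the documents do not rank them against LDH. These points limit the proposal but do not defeat it.

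**Conclusion.** The point holds as an inexpensive efficiency gain. Nothing in the primary analyses is wrong, and type I error is not threatened.

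For final-look OS power, the covariate form gives about 0 points if LDH is not prognostic, 0.5 to 1 at LDH HR 1.5, 2 to 3 at 2.0 and 4 to 7 at 2.5. The limited PFS runs point the same way. The gain matters only from about HR 2.0.

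These sizes rest on an assumed LDH effect and prevalence, on treatment effects defined within LDH level, and on near-complete baseline LDH. The documents supply none of these. The case for acting is that the expected loss is close to zero and the possible gain is several points on both primary endpoints.

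**What to change.** Before Analysis #1 and any efficacy unblinding:

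1. Keep the three strata. Add baseline LDH (at or below versus above ULN, latest value before first dose) as a covariate in the stratified Cox model for PFS, OS, iPFS and the OS subgroup.
2. Make that model's treatment score test the primary test and its treatment HR the primary estimate.
3. State a missing-LDH rule that keeps every randomized subject in the analysis, for example a missing category or a fixed assignment as is done for PD-L1.
4. Keep the unadjusted stratified log-rank as a sensitivity analysis.

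If the sponsor prefers the present analysis, one sentence saying why LDH is left out would be enough.

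**Cost.** A SAP revision and a short amendment of Protocol 10.5.2.2, with no new data. The primary test becomes model-based, and the reported HR becomes conditional on LDH and has to be described that way.
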